5.10.2. Analysis of NAb Data

The absolute occurrence (n) and percent of subjects (%) with NAb status in the NAb analysis set will be provided by treatment groups.

5.11. Association of Immunogenicity with Exposure and Safety

5.11.1. Immunogenicity and Exposure

Potential association between immunogenicity variables and systemic exposure to REGN10933, and REGN10987 will be explored by treatment groups. Plots of drug concentration time profiles may be provided to examine the potential impact of ADA response status, and titer on these profiles.

5.11.2. Immunogenicity and Safety

Potential association between immunogenicity variables and safety may be explored with a primary focus on the following safety events during the TEAE period:

- Infusion reactions
- Hypersensitivity (SMQ: Hypersensitivity [Narrow])
- Anaphylaxis (SMQ: Anaphylaxis [Narrow]).

6. DATA CONVENTIONS

The following analysis conventions will be used in the statistical analysis.

6.1. Definition of Baseline for Efficacy/Safety Variables

Definitions of baseline for efficacy variables are defined in Section 4.5.

For safety variables, baseline will be the latest available valid measurement taken prior to the administration of study drug.

6.2. Data Handling Convention for Efficacy Variables

Not applicable.

6.3. Data Handling Convention for Missing Data

If pre-dose virologic results from the qualitative test are missing, then results from post-dose sample may be used to determine the qualitative PCR status at baseline, as long as the sample was collected 2 hours or less after starting study drug infusion.

For categorical variables, patients with missing data will be included in calculations of percentages. Number of patients with missing data will be presented.

Handling of Medications with missing/partial dates

To determine whether a medication is prior or concomitant medication, the missing medication start date is estimated as early as possible up to first dose date, and the missing medication end date is estimated as late as possible up to Day 29. If the medication start date is missing, the onset day will not be imputed in medication listings.

Handling of Adverse events Severity and Relatedness

If the intensity of a SAE, AESI and grade 3 or 4 AEs is missing, it will be classified as "Grade 3" in the frequency tables by CTC grade of SAE and AESIs. If the assessment of relationship of the investigational product is missing, it will be classified as related to the investigational product.

Date of infusions

Date of infusion is the non-missing administration date filled in the Study Drug Administration-IV CRF. If the first dose of study drug administration date is missing (even after site is queried), then the dosing date will be imputed with the randomization date. If any subsequent study drug administration date is missing, the date of dispensation of study drug from IRT will be used.

6.4. Visit Windows

Data analyzed by-visit-analysis will be summarized by the study scheduled visits described in Appendix 10.1, "Schedule of Event". The analysis visit windows will be exhaustive so that all available values obtained from unscheduled visits, early termination visit (ETV) and end of treatment (EOT)/end of study (EOS) have the potential to be summarized. No analysis visit windows will be applied for the study scheduled visits nor for drug concentration/immunogenicity data.

CONFIDENTIAL

Page 39 of 61

The following analysis visit windows will be used to map the unscheduled visits, ETV and EOT visits for NP Swab for SARS-CoV-2 RT-qPCR, based on the study day during the double blind period:

Table 6:Time Window for Summary of NP Swab for SARS-CoV-2 RT-qPCR (Cohort
1 Patients; Cohort 3 Patients ≥ 18 Years)

Visit Label	Targeted Study Day	Analysis Window in Study Day
Baseline	1	≤ 1
Day 7	7	[2, 10]
Day 15	15	[11, 22]
Day 29	29	[23, 32]

Table 7:Time Window for Summary of NP Swab for SARS-CoV-2 RT-qPCR (Cohort
2 Patients; Cohort 3 Patients < 18 Years)	Visit Label	Targeted Study Day	Analysis Window in Study Day
Baseline	1	≤ 1
Day 3	3	[2, 4]
Day 7	7	[5, 10]
Day 15	15	[11, 22]
Day 29	29	[23, 32]

The following analysis visit windows will be used to map the unscheduled visits, ETV and EOT visits for laboratory and biomarker variables based on the study day during the double blind period:

Table 8:Time Window for Summary of Laboratory and Biomarker Variables except
Serum for Serology (Cohort 1 Patients; Cohort 3 Patients ≥ 18 Years)

Visit Label	Targeted Study Day	Analysis Window in Study Day
Baseline	1	≤ 1
Day 7	7	[2, 11]
Day 15	15	[12, 22]
Day 29	29	[23, 32]

Table 9:Time Window for Summary of Laboratory and Biomarker Variables except
Serum for Serology (Cohort 2 Patients and Cohort 3 Patients <18 Years with
Body Weight ≥ 10 kg)

Visit Label	Targeted Study Day	Analysis Window in Study Day
Baseline	1	≤ 1
Day 7	7	[2, 11]
Day 15	15	[12, 22]
Day 29	29	[23, 32]

CONFIDENTIAL

Table 10:Time Window for Summary of Serum for Serology (Cohort 1 Patients;
Cohort 3 Patients ≥ 18 Years; Cohort 2 patients and Cohort 3 Patients <18
Years with Body Weight ≥ 10 kg)

Visit Label	Targeted Study Day	Analysis Window in Study Day					
Baseline	1	≤ 1					
Day 29	29	[2, 32]					

Table 11:	Time Window for Summary of Laboratory and Biomarker Variables
	(Cohort 2 Patients with Body Weight < 10 kg)

Visit Label	Targeted Study Day	Analysis Window in Study Day
Baseline	1	≤ 1
Day 7	7	[2, 18]
Day 29	29	[19, 32]

In the event of multiple measurements of the same test in the same window, if the measurements are from different categories, the priority order is scheduled, early termination visit then unscheduled visit. For the measurements in the same category, the value measured nearest to the target day will be assigned to the window; if they are at the same distance to the target day, the latest one will be used. Extra assessments (laboratory data or vital signs associated with non-protocol clinical visits or obtained in the course of investigating or managing adverse events) will be included in listings, but not summaries except for the endpoint determination. If more than one laboratory value is available for a given visit, the first observation will be used in summaries and all observations will be presented in listings.

The determination of baselines and values at the end of treatment for both efficacy and safety variables will be based on scheduled available assessments and unscheduled available assessments.

6.5. **Pooling of Centers for Statistical Analyses**

Not applicable.

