11.4.5.2. Other Safety

Vital Signs

Vital signs (temperature, pulse, blood pressure, and respiration rate) will be summarized by baseline and change from baseline to each scheduled assessment time with descriptive statistics.

Laboratory Tests

Laboratory test results will be summarized by baseline and change from baseline to each scheduled assessment time with descriptive statistics.

Number and percentage of patients with a potentially clinically significant value (PCSV) at any post-randomization time point will be summarized for each clinical laboratory test for all patients and separately for patients in whom the PCSV criterion was normal or missing at baseline.

Shift tables based on baseline normal/abnormal and other tabular and graphical methods may be used to present the results for laboratory tests of interest.

Listings will be provided with flags indicating the out of laboratory range values.

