5.8.2. Clinical Laboratory Measurements

Laboratory measurements include clinical chemistry and hematology results, and will be converted to standard international units and US conventional units. Summaries of laboratory variables based on standard international units will include:

- Descriptive statistics of laboratory result and change from baseline to Day 29. Summary statistics will include the number of patients, mean, median, standard deviation, quartiles, minimum, and maximum.
- Number and percentage of patients with a potentially clinically significant value (PCSV) at any post-randomization time point will be summarized for each clinical laboratory test for all patients and separately for patients in whom the PCSV criterion was normal or missing at baseline.
- Shift tables based on baseline normal/abnormal and other tabular and graphical methods may be used to present the results for parameters of interest.

Listing of all laboratory parameters normal range and abnormal flag by patient and visit will be provided.

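### The SAP keeps adverse-event work-up labs out of summaries but counts clinically significant values at any time point, and its Day 29 wording for laboratory change differs from the protocol

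*SAP*

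**What the plan says.** SAP 6.4 (Visit Windows) sets apart one class of results: "Extra assessments (laboratory data or vital signs associated with non-protocol clinical visits or obtained in the course of investigating or managing adverse events". These "will be included in listings, but not summaries except for the endpoint determination". The SAP does not say which endpoints the exception covers.

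The same section makes the analysis windows exhaustive, and gives as its reason that off-schedule results may then enter a summary: "all available values obtained from unscheduled visits, early termination visit (ETV) and end of treatment (EOT)/end of study (EOS) have the potential".

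SAP 5.8.2 (Clinical Laboratory Measurements) plans two main summaries:

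- "Number and percentage of patients with a potentially clinically significant value (PCSV) at any post-randomization time point will be summarized", by test, for all patients and separately for those whose baseline was normal or missing on that criterion.
- "Descriptive statistics of laboratory result and change from baseline to Day 29".

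It also allows shift tables and requires a by-patient listing with abnormal flags.

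Protocol 11.4.5.2 (Other Safety) has the same any-time PCSV rule, but for change it says: "Laboratory test results will be summarized by baseline and change from baseline to each scheduled assessment time with descriptive statistics". SAP 1.2.4 states that nothing departs from the statistical section of amendment 8.

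SAP 6.3 adds that, for categorical variables, "patients with missing data will be included in calculations of percentages", with the number missing shown.

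**The concern.** A PCSV table is meant to catch the worst laboratory finding in each patient, whenever it occurred. Samples drawn because something went wrong are among those most likely to hold that finding. If the SAP 6.4 rule is applied to the PCSV table, the table no longer matches its own definition, and two programmers working from the same SAP could produce different counts.

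The Day 29 wording raises a second question. After a single infusion, the early time course is of most interest, and a summary limited to Day 29 would not show it.

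Safety and tolerability are a primary objective in cohorts 2 and 3 and a secondary objective in cohort 1, so the laboratory tables are part of the safety picture. They are not the named safety endpoints.

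**Working it through.** The plan states no figure to reproduce, so the check is a comparison of texts plus the visit schedule.

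**1. Does the listings-only rule reach the PCSV table?** SAP 5.8.2 presents the PCSV count as a summary, so the SAP 6.4 rule applies unless the exception saves it. SAP 4.6 names three safety endpoints: treatment-emergent SAEs through day 29, grade 2 or higher infusion-related reactions through day 4, and grade 2 or higher hypersensitivity through day 29. No laboratory measure is among them. On a plain reading, work-up values are therefore excluded from a table defined as covering any time point.

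**2. Which abnormalities depend on the rule?** Scheduled post-dose safety labs (schedules of events in both documents) fall as follows:

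| Group | Draws | Nominal gaps in days | Last gap with visit windows |
|---|---|---|---|
| Adults; under 18 years and at least 10 kg | Day 7 (±1), 15 (±3), 29 (±3) | 7−1 = 6; 15−7 = 8; 29−15 = 14 | 26−18 = 8 to 32−12 = 20 |
| Under 18 years and under 10 kg | Day 7 (±1), 29 (±3) | 7−1 = 6; 29−7 = 22 | 26−8 = 18 to 32−6 = 26 |

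An abnormality present at any of these draws enters the PCSV count even if it has gone by Day 29. What depends on the rule is an abnormality that starts and ends between draws, or one that peaks in a higher PCSV category between draws, and is recorded only in a work-up sample.

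**3. Do the exhaustive windows settle it?** Not fully.

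- Within a window, SAP 6.4 ranks scheduled values first, then early-termination, then unscheduled. An unscheduled value enters a by-visit summary only if the window holds nothing of higher rank.
- Protocol 9.1.3 uses unscheduled visits for repeat testing after abnormal labs and for SAE and AESI follow-up, and Protocol 9.2.7 requires significantly abnormal results to be repeated. One sample can thus be both unscheduled (eligible for summary) and extra (listing only). Nothing says which label wins.
- SAP 6.4 has two tie-break rules: nearest to the target day and then the latest, and elsewhere the first observation. Neither selects the worst value.

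**4. Do the adverse-event tables cover the gap?** In part. Protocol 10.1.1 records only targeted events. In adults, the relevant routes are SAEs, grade 2 or higher infusion-related or hypersensitivity reactions, and events leading to a medically-attended visit through day 29; cohort 1 also has new diagnoses. Grade 3 and 4 events are collected only under 18 years. An adverse-event table gives a term, not a value or a PCSV category.

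**5. Day 29 against each scheduled assessment.** The two texts differ, and SAP 1.2.4 declares no difference. Two cautions apply. The SAP follows amendment 8, while the protocol at hand is amendment 10 US; its amendment history lists no change to 11.4.5.2, so the mismatch probably existed in amendment 8 but needs confirming. Also, SAP Tables 8, 9 and 11 define a Day 7 laboratory window, and Tables 8 and 9 a Day 15 window, which suggests that through Day 29 was meant.

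**6. Direction between arms.** Protocol 3.3.1 reports SAEs in 4.0% on placebo, 1.1% on 2400 mg and 1.3% on 1200 mg. If work-up labs track SAEs, placebo patients would have about 4.0/1.1 = 3.6 or 4.0/1.3 = 3.1 times as many occasions for them. Including those labs could raise the placebo PCSV rate more than the active rates.

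**The case against.** The strongest reply is that the listings-only sentence sits in a paragraph on choosing values for visit windows, so the specific any-time rule in SAP 5.8.2 should govern the PCSV table. Keeping informative, non-protocol samples out of by-visit means is sound practice. Unscheduled values can be summarized, every result appears in a flagged listing, and serious events reach the adverse-event tables by their own route. On this view only a clarification is needed.

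Much of this stands. The exclusion is right for by-visit means, and the intended reading may well be the benign one. But the SAP does not say so, its sentence refers to summaries without limit, and its only exception is undefined.

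A reader might go further and infer that short-lived drug-related abnormalities vanish from the safety tables. The documents do not support that: anything present at a scheduled draw is counted in the PCSV table. A reader might also infer that the rule hides harm from the drug. The SAE rates in Protocol 3.3.1 point, if anywhere, to more work-up sampling on placebo.

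**Conclusion.** The point holds as an internal conflict in a stated analysis rule, together with a probable mismatch with the protocol on the change summary. It should be corrected, but it does not touch the primary efficacy analysis or the named safety endpoints.

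The size cannot be derived. It depends on how many patients had a clinically significant value only in a work-up sample, and the documents give no basis for that number. A percentage built from the draw schedule would be misleading. For an abnormality with uniform onset over days 2 to 29, draws on days 7, 15 and 29 would catch 3/28 = 11% if it lasted 1 day and 24/28 = 86% if it lasted 10. Such figures turn on the assumed duration and onset, and they measure how often blood is drawn, not what the SAP rule removes.

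The denominator convention in SAP 6.3 is a minor matter. It lowers a percentage when patients lack post-dose values, but the number missing is presented, so a reader can recompute the rate.

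The conclusion rests on reading the SAP 6.4 sentence as written and on amendment 8 carrying the same text as the current Protocol 11.4.5.2.

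**What to change.** Amend the SAP as follows:

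- **5.8.2:** State that the PCSV count and any worst-value shift tables use all post-dose results, including unscheduled and adverse-event-driven ones.
- **6.4:** Limit the listings-only rule to by-visit summaries. Define the exception by naming the endpoints it covers, or delete it. Keep one tie-break rule.
- **5.8.2:** Replace the Day 29 wording with change to each scheduled visit, after checking amendment 8; if a restriction to Day 29 was intended, declare it in 1.2.4.
- **Tables:** Show a scheduled-only PCSV table beside the all-results table. Sicker patients, probably more of them on placebo, will have more extra samples; the comparison shows how much of any difference between arms comes from unequal sampling.
- **Optional:** State the PCSV denominator, for example patients with at least one post-dose value for that test.

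The cost is a few lines of SAP text and one extra table. No new data are needed.

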The Gamma family alpha spending function (Hwang, Shih, DeCani 1990) based on the primary endpoint of proportion of patients with \geq 1 COVID-19-related hospitalization or all-cause death through day 29 for the 1200 mg versus placebo comparison will be used to control for type I error for the planned interim analysis and the final analysis. The parameter for the Gamma family spending function will be calculated based on the information fraction of the interim analysis such that the alpha level at the interim analysis is equal to 0.01. If the interim analysis is not significant at 0.01 level for an endpoint, the remaining alpha level will be calculated based on the gamma parameter and information fraction. The information fraction will be determined based on the sample size in the mFAS at the interim analysis and final analysis of the primary endpoint for the 1200 mg group versus placebo comparison as follows: number of patients randomized to 1200 mg or placebo on or before 17 January 2021 in the mFAS divided by number of patients randomized to 1200 mg or placebo treatment group was dropped per IDMC recommendation) in the mFAS.

Cohort 2 and 3

An interim descriptive analysis of phase 3 cohort 2 and 3 may be conducted for regulatory purposes when the phase 3 cohort 1 primary analysis is performed.

10. APPENDIX

10.1. Schedule of Time and Events

Schedule of Events: Phase 3 (Cohort 1 Patients; Cohort 3 Patients ≥18 Years)

		Screening/Baseline Visit ¹				Follow Up ³									
Day		-1 t	io 1		n	3	4	7	15	22	20	60	00	120	160
		Pre-Dose	Dose	Post-Dose	2	5	-	/	13	22	2)	00	70	120	107
Visit Number		1			2	3	4	5	6	7	8	9	10	11	12
Window (Days)								± 1	± 3	± 3	± 3	± 3	± 3	$\pm 7^{12,14}$	$\pm 7^{14}$
Screening/Baseline Only															
Informed consent	Х														
PGx sub-study consent (optional) ⁴	Х														
Immunoprofiling sub-study consent (optional) ⁴	Х														
Inclusion/exclusion	Х														
Antigen or molecular diagnostic test for SARS-CoV-2 ⁵	Х														
Demographics	Х														
Medical history (including COVID-19 illness, risk factors)	Х														
Weight and height	Х														
Randomization (treatment assignment)		Х													
Treatment															
Study drug administration			Х												
Efficacy															
Query for COVID-19-related medically-attended visit details								Х	Х	Х	Х				
NP swab for SARS-CoV-2 RT-qPCR		Х						Х	Х		Х				
Safety															
Vital signs		X ⁶		X ⁶											
Treatment-emergent grade ≥ 2 IRRs ^{7,8}			Х	Х	$\leftarrow cc$	ont. mo	n. →								
TEAEs that led to any medically-attended visit ^{7,8}				Х	←	- contii	nuous r	noni	torin	g →					
Treatment-emergent grade ≥ 2 hypersensitivity ^{7,8}			Х	Х	←	- contii	nuous r	noni	torin	$g \rightarrow$					
Treatment-emergent SAEs ^{7,8,16} X X		\leftarrow continuous monitoring \rightarrow													
Targeted concomitant medications ^{7, 8} X X X		Х	\leftarrow continuous monitoring \rightarrow												
Concomitant procedures ^{7,8}	Х		Х	Х			← c	ontir	nuou	s mo	nitor	ring -	\rightarrow		

Regeneron Pharmaceuticals, Inc.

CONFIDENTIAL

$ \begin{array}{ c c c c c c c c c c c c c c c c c c c$								
ScreenPre-DoseDosePost-Dose23456789101112Visit Number123456789101112Window (Days) ± 1 ± 3 $\pm 7^{12,14}$ $\pm 7^{14}$ Vital status ¹⁶ ± 1 ± 3 ± 3 ± 3 ± 3 ± 3 $\pm 7^{12,14}$ $\pm 7^{14}$ Pregnancy test (women of childbearing potential) ⁹ X $=$								
Visit Number123456789101112Window (Days) ± 1 ± 3 $\pm 7^{12,14}$ $\pm 7^{14}$ Vital status ¹⁶ XXPregnancy test (women of childbearing potential) ⁹ XXXPregnancy status ¹⁶ XXXSafety information (newborns of study participants) ¹⁶ XXXXCentral Laboratory Safety TestingX ¹⁰ XXXXXXXXXXXXBlood chemistry (including differential)X ¹⁰ XXXX								
Window (Days) $\pm 1 \pm 3 \pm 3 \pm 3 \pm 3 \pm 3 \pm 3 \pm 7^{12,14} \pm 7^{14}$ Vital status ¹⁶ IIIXXPregnancy test (women of childbearing potential) ⁹ XIIIXXPregnancy status ¹⁶ IIIIIIIIPregnancy status ¹⁶ IIIIXXXSafety information (newborns of study participants) ¹⁶ IIIIXXXCentral Laboratory Safety TestingHematology (including differential)X ¹⁰ XXXIIBlood chemistry (including AST, ALT, CRP, LDH)X ¹⁰ XXXIICoagulation tests (D-dimer, PT/INR, aPTT)X ¹⁰ XXXIICentral Laboratory Immunogenicity Testing (Not Enrolled in PK Sub-Study, Not Pregnant at Randomization)Serum for ADA ¹³ X ¹³ XXI								
Vital status ¹⁶ Image: Marcon Status St								
Pregnancy test (women of childbearing potential)XIIIIIIPregnancy status ¹⁶ IIIIIXXSafety information (newborns of study participants) ¹⁶ IIIIIXXCentral Laboratory Safety TestingHematology (including differential)X ¹⁰ XXXXIBlood chemistry (including AST, ALT, CRP, LDH)X ¹⁰ XXXXIICoagulation tests (D-dimer, PT/INR, aPTT)X ¹⁰ XXXXIICentral Laboratory Immunogenicity Testing (Not Enrolled in PK Sub-Study, Not Pregnant at Randomization)XXIISerum for ADA ¹³ X ¹³ IXXIII								
$\begin{array}{c c c c c c c c c c c c c c c c c c c $								
$ \begin{array}{c c c c c c c c c c c c c c c c c c c $								
Central Laboratory Safety Testing Hematology (including differential) X ¹⁰ X X X X Image: Colspan="5">Comparison of the colspan="5">X X X X X X X X X X X <th< td=""></th<>								
Hematology (including differential) X^{10} XXXXBlood chemistry (including AST, ALT, CRP, LDH) X^{10} XXXXCoagulation tests (D-dimer, PT/INR, aPTT) X^{10} XXXXCentral Laboratory Immunogenicity Testing (Not Enrolled in PK Sub-Study, Not Pregnant at Randomization)Serum for ADA ¹³ XXXX								
Coagulation tests (D-dimer, PT/INR, aPTT) X ¹⁰ X X X X I Central Laboratory Immunogenicity Testing (Not Enrolled in PK Sub-Study, Not Pregnant at Randomization) X X X I I Serum for ADA ¹³ X ¹³ X X X X X X X								
Central Laboratory Immunogenicity Testing (Not Enrolled in PK Sub-Study, Not Pregnant at Randomization) Serum for ADA ¹³ X X								
Serum for ADA ¹³ X ¹³ X								
Central Laboratory Drug Concentration and Immunogenicity Testing (Enrolled in PK Sub-Study, Not Pregnant at Randomization)								
Serum for drug concentration (PK) ¹² $X^{10,12}$ X^{12} X^{12}								
Serum for ADA ¹³ X ¹³ X ¹³ X ¹³								
Central Laboratory Drug Concentration and Immunogenicity Testing (Pregnant at Randomization)								
Serum for drug concentration (PK) ¹² $X^{10,12}$ X^{12} X^{12}								
Serum for ADA ¹³ X^{13} X^{13}								
Central Laboratory Biomarker Testing								
Serum for serology X ¹⁰ X								
Serum for research X ¹⁰ X X X								
Plasma for research X ¹⁰ X X X								
Exploratory Patient-reported Outcomes								
SE-C19 ¹⁴ X Daily								
PGIS ¹⁴ X Daily								
PGIC ¹⁴ X								
Item: return to usual health X Daily								
Item: return to usual activities X Daily								
EQ-5D-5L ¹⁴ X Daily X^{14} X^{14} X^{14} X^{14} X^{14}								
WPAI+CIQ X X X X X V								
Immunoprofiling (Optional Sub-Study)								
Blood for PBMCs X X V								

Regeneron Pharmaceuticals, Inc.

Day		Screening/Baseline Visit ¹			Follow Up ³										EOS ³
		-1 to 1		2	2	4	7	15	22	20	60	00	120	160	
	Screen	Pre-Dose	Dose	Post-Dose	2	3	Ŧ		15	22	29	00	90	120	109
Visit Number		1			2	3	4	5	6	7	8	9	10	11	12
Window (Days)								± 1	± 3	$\pm 7^{12,14}$	$\pm 7^{14}$				
Pharmacogenomics (Optional Sub-Study)															
Blood for DNA ⁴		X ⁴													
Blood for RNA ⁴		X^4													

ADA, anti-drug antibodies; AE; adverse event; ALT, alanine transaminase; aPTT, activated partial thromboplastin time; AST, aspartate transaminase; CRP, c-reactive protein; EOS, end of study; INR, international normalized ratio; IRR, infusion-related reaction; LDH, lactate dehydrogenase; NP, nasopharyngeal; PBMC, peripheral blood mononuclear cells; PGx, pharmacogenomics; PK, pharmacokinetics; PT, prothrombin time; SAE, serious adverse event; RT-qPCR, quantitative reverse transcription polymerase chain reaction; TEAE, treatment-emergent adverse event.

Schedule of Events: Phase 3 (Cohort 2 Patients; Cohort 3 Patients <18 Years)

Day		Screening/Baseline Visit ¹			Follow Up ³										EOS ³
Day		-1 to	o 1		2	3	4	7	15	22	20	60	00	120	160
	Screen	Pre-Dose	Dose	Post-Dose	2	3			15	22	2)	00	70	120	107
Visit Number		1			2	3	4	5	6	7	8	9	10	11	12
Window (Days)								± 1	± 3	± 3	± 3	± 3	± 3	$\pm 7^{14}$	$\pm 7^{14}$
Screening/Baseline Only															
Parental informed consent and informed assent	Х														
Inclusion/exclusion	Х														
Antigen or molecular diagnostic test for SARS-CoV-2 ⁵	Х														
Demographics	X														
Medical history (including COVID-19 illness, risk factors)	Х														
Weight and height	Х														
Randomization (treatment assignment)		Х													
Randomization (PK-ADA schedule assignment) ¹⁵		Х													
Treatment															
Study drug administration			Х												
Efficacy															
Query for COVID-19-related medically-attended visit details		Х						Х	Х	Х	Х				
NP swab for SARS-CoV-2 RT-qPCR		Х				Х		Х	Х		Х				
Safety		-				-	-		-		-				
Vital signs (≥12 years)		X ⁶		X ⁶											
Vital signs (<12 years)		X ⁶	X ⁶	X ⁶											
Treatment-emergent grade ≥ 2 IRRs ^{7, 8}			Х	X ¹⁷	+	– cont. 1	non. \rightarrow								
TEAEs that led to any medically-attended visit ^{7, 8}				X ¹⁷		$\leftarrow cor$	ntinuous m	onite	oring	$J \rightarrow$					
Treatment-emergent grade ≥ 2 hypersensitivity ^{7, 8}			Х	X ¹⁷		← cor	ntinuous m	onito	oring	$g \rightarrow$					
Treatment-emergent grade 3 or 4 AEs ⁸			Х	X ¹⁷		← cor	ntinuous m	onito	oring	$J \rightarrow$					
Treatment-emergent SAEs ^{7, 8,16}			Х	X ¹⁷			`← cc	ontin	uous	mor	nitori	ng –	→		
Targeted concomitant medications ^{7,8}	Х		Х	X ¹⁷	$\leftarrow \text{ continuous monitoring} \rightarrow$										
Concomitant procedures ^{7,8}	Х		Х	X ¹⁷	\leftarrow continuous monitoring \rightarrow										
Vital status ¹⁶														Х	Х
Pregnancy test (women of childbearing potential) ⁹	X														
Pregnancy status ¹⁶														Х	Х

Regeneron Pharmaceuticals, Inc.

CONFIDENTIAL

Davi	Screening/Baseline Visit ¹			Follow Up ³										EOS ³	
Day		-1 to	o 1		r	3	1	7	15	22	20	60	00	120	160
	Screen	Pre-Dose	Dose	Post-Dose	4	3	4	/	15	22	29	00	90	120	109
Visit Number		1			2	3	4	5	6	7	8	9	10	11	12
Window (Days)								± 1	± 3	± 3	± 3	± 3	± 3	$\pm 7^{14}$	$\pm 7^{14}$
Safety information (newborns of study participants) ¹⁶														Х	Х
Central Laboratory Safety Testing and Central Laboratory Biomarker Testing, Body Weight ≥20 kg															
Hematology (including differential)	-	X ¹⁰						Х	Х		Х				
Blood chemistry (including AST, ALT, CRP, LDH)	-	X^{10}						Х	Х		Х				
Serum for serology	-	X^{10}									Х				
Serum for exploratory research		X^{10}						Х	Х		Х				
Plasma for exploratory research		X^{10}						Х	Х		Х				
Central Laboratory Safety Testing and Central Laboratory Biomarker Testing, Body Weight ≥10 kg to <20 kg															
Hematology (including differential)		X^{10}						Х	Х		Х				
Blood chemistry (including AST, ALT, CRP, LDH)		X^{10}						Х	Х		Х				
Serum for serology		X^{10}									Х				
Central Laboratory Safety Testing and Central Laboratory Biomarker Testing, Body Weight <10 kg															
Hematology (including differential)		X^{10}						Х			Х				
Blood chemistry (including AST, ALT, CRP, LDH)		X^{10}						Х			Х				
Serum for serology		X^{10}													
Central Laboratory Drug Concentration and Immunogen	nicity Tes	ting (All B	ody W	eight Tiers)										
Serum for PK-ADA (Schedule A) ¹⁵	Х	10,12		X ¹²		X ¹²					\mathbf{X}^{12}				
Serum for PK-ADA (Schedule B) ¹⁵	X	10,12		X ¹²				X^{12}			X^{12}				
Serum for PK-ADA (Schedule C) ¹⁵	Х	10,12		X ¹²					X^{12}		\mathbf{X}^{12}				
Serum for PK-ADA (Schedule D) ¹⁵	X	10,12		X ¹²						X^{12}	X^{12}				
Exploratory Patient-reported Outcomes (Age ≥12 Years 0	Only) ¹⁴														
SE-C19 ¹⁴		Х					Dail	у							
PGIS ¹⁴		Х					Dail	у							
PGIC ¹⁴											Х				
Item: return to usual health		Х			Daily										
Item: return to usual activities		Х			Daily										
EQ-5D-Y-5L ¹⁴		Х					Dail	у				X^{14}	X ¹⁴	X ¹⁴	X ¹⁴
WPAI+CIQ								Х	Х	Х	Х				

Regeneron Pharmaceuticals, Inc.

CONFIDENTIAL

Day	Screening/Baseline Visit ¹				Follow Up ³										EOS ³
Day	-1 to 1			r	3	4	7	15	22	20	60	00	120	160	
	Screen	Pre-Dose	Dose	Post-Dose	2	3	4		15	22	29	00	90	120	109
Visit Number		1			2	3	4	5	6	7	8	9	10	11	12
Window (Days)								± 1	± 3	$\pm 7^{14}$	$\pm 7^{14}$				

ADA, anti-drug antibodies; AE; adverse event; ALT, alanine transaminase; aPTT, activated partial thromboplastin time; AST, aspartate transaminase; CRP, c-reactive protein; EOS, end of study; INR, international normalized ratio; IRR, infusion-related reaction; LDH, lactate dehydrogenase; NP, nasopharyngeal; PGx, pharmacogenomics; PK, pharmacokinetics; PT, prothrombin time; SAE, serious adverse event; RT-qPCR, quantitative reverse transcription polymerase chain reaction; TEAE, treatment-emergent adverse event.

- 1. Screening visit may occur on the same day as, or the day prior to, the baseline visit.
- 2. [Phase 1 footnote removed]
- 3. On visit days where in-person sample collections or assessments are not required, information may be collected by phone.
- 4. Patients (cohort 1; cohort 3 ≥18 years old) must provide separate consent to collect blood samples as part of the optional pharmacogenomics (PGx) sub-study. Blood sample for RNA may be collected at day -1 or day 1 (ie, screening or pre-dose) but must be collected prior to randomization. Blood sample for DNA should be collected at the day -1 or day 1 visit, but may be collected at any visit. Refer to Section 9.2.12 for more information about the PGx sub-study.

Patients (cohort 1; cohort $3 \ge 18$ years old) must provide separate consent to collect blood samples as part of the optional peripheral blood mononuclear cell (PBMC) sub-study. Blood samples for PBMCs must be collected at the visits indicated. Refer to Section 9.2.11 for more information about this sub-study.

- 5. Refer to Section 9.2.1.2 for diagnostic test requirements during screening.
- 6. Vital signs, including temperature, blood pressure, heart rate, and SpO₂ will be collected as described in Section 9.2.4.1.

For patients in cohort 1 and patients \geq 12 years in cohort 2 and cohort 3, vital signs will be taken once before the infusion and once after the infusion is completed. After infusion of study drug, these patients will be observed for at least 1 hour.

For patients in **patients** <12 years in cohort 2 and cohort 3, vital signs will be taken before infusion, approximately every 30 minutes during the infusion, after the infusion is completed, approximately 1 hour post-infusion, and approximately 2 hours post-infusion. After infusion of study drug, these patients will be observed for at least 2 hours.

7. Treatment-emergent AESIs (grade ≥2 IRRs, grade ≥2 hypersensitivity, and TEAEs associated with *any* medically-attended visit) and treatment-emergent SAEs will be recorded until day 29. From day 30 to day 169, only treatment-emergent SAEs will be recorded. For patients in cohort 2 and patients <18 years in cohort 3, treatment-emergent grade 3 or 4 AEs will also be recorded until day 29. Refer to Section 10 for more information on reporting and recording requirements.

Regeneron Pharmaceuticals, Inc.

Targeted concomitant medications and concomitant procedures will also be reviewed and recorded. Refer to Section 9.2.4.3 for more information.

- 8. Continuously-monitored events will be recorded when they occur during the corresponding time period marked on the schedule of events. Study visits (including phone calls) are not required solely to collect continuously-monitored assessments, if no other assessments are planned on that day.
- 9. Pregnancy testing will be performed in women of childbearing potential (WOCBP) only and regardless of pregnancy status. A negative test is **not required** prior to study drug administration. Serum or urine pregnancy test are both acceptable. Refer to Section 9.2.6 for more information, including a definition of WOCBP.

Note that a paper pregnancy report form must be completed for each patient who becomes pregnant or is pregnant at the signing of consent.

- 10. The indicated blood samples may be collected at the either day -1 or day 1 (ie, screening or pre-dose), but must be collected prior to randomization. For patients in phase 3 cohort 2, efforts should be made to collect all screening/pre-dose blood samples on the same study visit, when feasible.
- 11. [Footnote removed]
- 12. Actual dosing time and drug concentration sample collection times, as applicable, will be recorded.

At the screening/baseline visit, blood for assessment of drug concentration in serum will be taken prior to dosing and within 60 minutes after the end of infusion (EOI). The EOI sample should be collected from the arm contralateral to that used for IV infusion. If not medically feasible, the EOI sample can be drawn from the same arm, but not from the infusion catheter.

In cohort 1 and cohort 3 (\geq 18 years old), patients will follow different blood sample collection schedules for drug concentration and immunogenicity depending on whether they enrolled in the PK sub-study (cohort 1), not enrolled in the PK sub-study (cohort 1), or are pregnant at randomization (cohort 3 patients \geq 18 years old). For samples collected on day 120, the collection window is \pm 28 days. Refer to Section 9.2.8 for more information on the PK sub-study.

- 13. The window for predose ADA sample collection is as close to administration of study drug as is reasonable. Actual dosing time and ADA sample collection times, as applicable, will be recorded.
- 14. Patients in cohort 1 and patients ≥12 years in cohort 2 and cohort 3 will self-report symptoms using electronic surveys. The order of completion is as follows: SE-C19, PGIS, PGIC, return to usual health, return to usual activities, EQ-5D-5L, WPAI+CIQ. On days when a survey/questionnaire is not required it will be skipped, but the overall order will remain the same. Note that the WPAI+CIQ, EQ-5D-5L, and EQ-5D-Y-5L will only be administered at sites when regionally available.

Regeneron Pharmaceuticals, Inc.

On days 60, 90, 120, and 169, the window for electronic survey/questionnaire assessment is ± 3 days. Note that study visits are not required on days when only electronic survey data are collected.

- 15. In **cohort 2 (and patients <18 years in cohort 3)**, each patient will be assigned at randomization by IWRS to a blood sample collection schedule for drug concentration and immunogenicity analysis. Actual dosing time and PK-ADA sample collection times will be recorded. To conserve blood volume, a single blood draw for drug concentration and immunogenicity will be obtained.
- 16. Patients will be followed by phone at day 120 and day 169 for vital status, pregnancy status, targeted safety information, and additional safety information in newborns of study participants. Refer to Section 9.2.5 for more information on these follow-up assessments.
- 17. For patients <12 years in cohort 2 and cohort 3, follow-up by phone will be conducted within 6 to 8 hours of infusion to collect the information indicated.

Parameter	PCSV	Comments
Clinical Chemis	try	
ALT*	>3 and \leq 5 ULN and baseline \leq 3 ULN*	Enzymes activities must be expressed in ULN, not in IU/L.
	>5 and ≤ 10 ULN and baseline ≤ 5 ULN	Concept paper on DILI – FDA draft Guidance Oct 2007.
	>10 and ≤ 20 ULN and baseline ≤ 10 ULN	Each category is calculated independently.
	>20 ULN and baseline ≤ 20 ULN	* At least one level is required; multiple levels are optional for phase 2/3 studies. If it is desirable to get the distribution across the different PCSV levels, additional shift table on $\leq 3, >3$ to $\leq 5, > 5$ to $\leq 10, >10$ to ≤ 20 , and > 20 category for baseline vs. post baseline may be provided
AST*	 >3 and ≤ 5 ULN and baseline ≤ 3 ULN* >5 and ≤ 10 ULN and baseline ≤ 5 ULN >10 and ≤ 20 ULN and baseline ≤ 10 ULN 	Enzymes activities must be expressed in ULN, not in IU/L. Concept paper on DILI – FDA draft Guidance Oct 2007. Each category is calculated independently.
	>20 ULN and baseline ≤ 20 ULN	* At least one level is required, multiple levels are optional for phase 2/3 studies. If it is desirable to get the distribution across the different PCSV levels, additional shift table on $\leq 3, >3$ to $\leq 5, > 5$ to $\leq 10, >10$ to ≤ 20 , and > 20 category for baseline vs. post baseline may be provided
Alkaline Phosphatase	>1.5 ULN and baseline \leq 1.5 ULN	Enzyme activity must be expressed in ULN, not in IU/L. Concept paper on DILI – FDA draft Guidance Oct 2007.

